5 ABBREVIATIONS

Abbreviation	Term
2x/week	Twice a week
ACTH	Adrenocorticotropic hormone
ACR	American College of Rheumatology
ACR20	20% improvement in ACR criteria
ACR50	50% improvement in ACR criteria
ACR70	70% improvement in ACR criteria
AE	Adverse event
ALT	Alanine aminotransferase
ANC	Absolute neutrophil count
AST	Aspartate aminotransferase
CDAI	Clinical Disease Activity Index
CFR	Code of Federal Regulations
CIA	Collagen-induced arthritis
CRP	C-reactive protein
CTX-I	C-terminal crosslinking telopeptide of Type I collagen
CTX-II	C-terminal crosslinking telopeptide of Type II collagen
DA	Disease activity
DMARD	Disease modifying antirheumatic drug
eCRF	Electronic case report form
DAS28-ESR	Disease Activity Score with 28 joint count and ESR
ED	Emergency Department
ESR	Erythrocyte sedimentation rate
EULAR	European League Against Rheumatism
FACIT-F	Functional Assessment of Chronic Illness Therapy-Fatigue
FDA	Food and Drug Administration
GCP	Good Clinical Practices
HAQ-DI	Health Assessment Questionnaire-Disability Index
HbA1c	Glycosylated hemoglobin
HBsAg	Hepatitis B surface antigen
HBcAb	Hepatitis B core antibody
HCV	Hepatitis C virus antibody
HCV PCR	Hepatitis C virus polymerase chain reaction
HIPAA	Health Insurance Portability and Accountability Act
ICF	Informed consent form
ICTP	I collagen telopeptide
ICH	International Conference on Harmonisation
ID	Identification
IEC	Independent Ethics Committee
IGRA	Interferon gamma release assay
IMP	Investigational medicinal product

Abbreviation	Term
IRB	Institutional Review Board
IXRS	Interactive Phone/Web Response System
JAK	Janus kinase
LDA	Low disease activity
MCR	Melanocortin receptor
mITT	Modified intent to treat
MM	Medical monitor
MTX	Methotrexate
OPG	Osteoprotegerin
PINP	N-terminal propeptide of Type I collagen
QD	Per day, daily
RA	Rheumatoid arthritis
RANKL	Receptor activator of nuclear kappa β ligand
SAE	Serious adverse event
SC	Subcutaneous
TB	Tuberculosis
TNF- α	Tumor Necrosis Factor-alpha
TEAE	Treatment-emergent adverse event
U	Unit(s)
US	United States of America
ULN	Upper limit of normal
VAS	Visual Analog Scale
WPAI	Work Productivity and Activity Impairment Questionnaire

Study Title: A Multicenter, 2 Part Study to Assess the Efficacy and Safety of Acthar Gel in Subjects With Rheumatoid Arthritis With Persistently Active Disease	
Protocol Number: MNK14294063	Type: Phase 4 (US)/Phase 2 (all other countries)
Condition/Disease:	Rheumatoid Arthritis
contraindication as per the United States (US) Prescribing Information for Acthar. Subjects cannot have any history of Type 1 or Type 2 diabetes, or have any clinically significant infection.	

Concomitant Medications/Nondrug Therapies:
 
Subjects must remain on their current stable doses of DMARDs and corticosteroid throughout the study. Intraarticular corticosteroids; live or live-attenuated vaccines; enteral or parenteral immunosuppressive medications including, but not limited to azathioprine, cyclophosphamide, cyclosporine, tacrolimus, mycophenolare mofetil, rituximab (or other B-cell inhibitors); and any investigational drug, device, or procedure administered as part of a research study are prohibited during this study.
 
Opioid use is allowed during the study but prohibited in the 24 hours prior to each study visit.
 
All medications (including vaccinations) and nondrug therapies (eg, blood transfusions, oxygen supplementation) received by subjects from the Screening Visit through the Follow-up Visit will be recorded.
	

Investigational Medicinal Product and Treatment Administration:
 
Acthar contains a highly purified porcine ACTH analogue currently approved by the Food and Drug Administration (FDA) in multiple indications. Acthar and its matching placebo will be supplied by the sponsor and administered SC as follows in this study:
 
Part 1 (Open Label Period):
 
Acthar 1 mL (80 U) administered 2x/week for 12 weeks.
 
Part 2 (Randomized Maintenance Period):
 
Acthar 1 mL (80 U) administered 2x/week for 12 weeks, OR Placebo 1 mL administered 2x/week for 12 weeks.
	

Efficacy Evaluations:
 
The following efficacy assessments will be evaluated: DAS28-ESR, ACR core criteria for defining RA improvement, Clinical Disease Activity Index (CDAI), Health Assessment Questionnaire-Disability Index (HAQ-DI), and the Functional Assessment of Chronic Illness Therapy- Fatigue (FACIT-F).
	

[REDACTED]
	

[REDACTED]
	

Safety Evaluations:
 
The following safety assessments will be evaluated: adverse events, physical examinations, clinical laboratory tests, pregnancy testing, and vital signs.
	

Statistical Methods:
 
Analysis Populations
 
 The Modified Intent to Treat (mITT) Population will include all enrolled subjects who receive 1 or more doses of study drug and who contribute any efficacy data to the study. 	

Study Title: A Multicenter, 2 Part Study to Assess the Efficacy and Safety of Acthar Gel in Subjects With Rheumatoid Arthritis With Persistently Active Disease

Protocol Number: MNK14294063

Type: Phase 4 (US)/Phase 2 (all other countries)

Condition/Disease:

Rheumatoid Arthritis

- The Per-Protocol Population will include the subset of the mITT population who complete the study as per protocol.
- The Safety Population will include all enrolled subjects who receive 1 or more doses of study drug.

Sample Size

It is expected that 360 subjects will be screened and a total of 232 subjects will be enrolled in this study. It is estimated that 55% of subjects will either drop out before Week 12 or will not achieve LDA by Week 12. The remaining 45% of subjects will have achieved LDA after 12 weeks of treatment with Acthar and will be randomized into 2 treatment groups in Part 2 of the study. Based on results from previous studies, it is estimated that 80% of the Acthar group and 50% of the placebo group will maintain LDA after the 12 additional weeks of treatment. Assuming that 52 subjects per group (104 subjects total) will complete Part 2, and based on the use of a 2-sided, 2-sample comparison of proportions at the alpha = 0.05 level of significance, there will be 90% of power to detect a difference in the 2 treatment groups.

Efficacy

For the primary endpoint, the proportion of subjects with LDA at Week 12 along with a 2-sided 95% confidence interval will be provided. The lower bound of the 95% confidence interval will be used to evaluate the response rate. The study will be deemed successful if the lower bound of the 95% confidence interval is $\geq 10\%$.

For the secondary endpoints, the proportions of subjects who maintain LDA in Part 2 for the 2 treatment groups will be compared using a 2-sided Pearson's chi-square test at a significance level of 0.05. The time to disease activity flare in Part 2 will be analyzed using log-rank test. The proportion of subjects with CDAI ≤ 10 at Week 12 and the proportion of subjects who meet criteria for ACR 20 at Week 12 will be analyzed using the same method as that for the primary endpoint.

For the exploratory endpoints,

[Redacted text block]

[figure not shown]
Safety

Treatment-emergent adverse events and serious adverse events will be summarized using the appropriate version of MedDRA by preferred term within system organ class. Other safety data will be listed and summarized descriptively or graphically, as appropriate.

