11 STUDY DESIGN

11.1 Description

This is a multicenter, multiple dose study to examine the effect of Acthar in adult subjects with RA with persistently active disease. Approximately 232 subjects will be enrolled.

During the first part of the study (Part 1-Open Label Period) all enrolled subjects will be treated with Acthar 1 mL (80 U) SC 2x/week for 12 weeks to assess the proportion of subjects who achieve LDA.

After 12 weeks of Acthar treatment, subjects who have achieved LDA (defined as DAS28-ESR < 3.2) will enter a double-blind randomized maintenance period (Part 2-Randomized Maintenance Period) and will be randomized in a 1:1 ratio into 2 groups:

- Group 1: Acthar 1 mL (80 U) SC 2x/week for an additional 12 weeks.
- Group 2: Placebo 1 mL SC 2x/week for an additional 12 weeks.

Subjects who do not achieve LDA at Week 12 will be discontinued from the study.

Subjects who experience a flare in disease activity will be discontinued from the study. Flare or worsening of disease activity is defined as:

- **Weeks 0 to 11:** DAS28-ESR ≥ 3.2 and increase of > 0.6 from the Week 0 assessment sustained over 2 consecutive study visits; **or** DAS28-ESR ≥ 3.2 and increased of > 1 from the Week 0 assessment at a single visit.
- **Weeks 13 to 23:** DAS28-ESR < 3.2 and increase of 1.2 from the Week 12 assessment; **or** DAS28-ESR ≥ 3.2 and increased of > 0.6 from the Week 12 assessment sustained over 2 consecutive study visits; **or** DAS28-ESR ≥ 3.2 and increase of > 1 from the Week 12 assessment at a single visit ([van der Maas, 2013](#)).

All subjects will have a Follow-up Visit 28 (± 2) days after their last dose of study drug.

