12 SELECTION OF SUBJECTS

12.1 Inclusion Criteria

Subjects must meet all of the following criteria for inclusion in the study at the Screening Visit and the Baseline Visit.

1. Subjects must be adequately informed and understand the nature and risks of the study and must be able to provide a signature and date on the ICF.
2. Subjects must be ≥ 18 years of age at Screening Visit and can be male or female.
3. Female subjects must be of nonchildbearing potential (history of hysterectomy, bilateral oophorectomy, or postmenopausal with no history of menstrual flow in the 12 months prior to the Screening Visit), or if of childbearing potential must be nonpregnant, nonlactating and agree to use effective contraception with a male partner throughout study participation (through the Follow-up Visit). Acceptable forms of contraception include hormonal measures (oral contraceptive pills, contraceptive patch, contraceptive ring, injections), intrauterine devices, double barrier method (condom plus diaphragm, condom or diaphragm plus spermicidal gel or foam), and abstinence.
4. Male subjects with a female partner of childbearing potential must have been surgically sterilized (vasectomy) or agree to use a double barrier method for contraception (condom plus diaphragm, condom or diaphragm plus spermicidal gel or foam) or remain abstinent throughout their study participation (through the Follow-up Visit).
5. Subjects must meet the criteria for RA as defined by the 2010 ACR/EULAR classification at the Screening Visit ([Aletaha et al, 2010](#)).
6. Subjects must have persistently active RA defined as a DAS28-ESR > 3.2 despite treatment with required biologic/nonbiologic DMARD(s) and a corticosteroid as defined below at the Screening and Baseline Visits.

7. Subjects must have been on a corticosteroid in the 12 weeks prior to the Screening Visit and on a stable dose of 5 mg to 10 mg of prednisone (or prednisone equivalent) for 4 weeks prior to the Screening Visit.
8. Subjects must have been on 1 of the following:
 - MTX \leq 20 mg per week and 1 additional allowed biologic or nonbiologic DMARD for at least 12 weeks prior to the Screening Visit and must remain on those doses throughout the study, OR
 - One allowed biologic DMARD for at least 12 weeks prior to the Screening Visit and must remain on that dose throughout the study.

Table 12-1 Allowed DMARDs

Allowed Nonbiologic DMARDs	Allowed Biologic DMARDs

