20.3 Endpoints

20.3.1 Primary Efficacy Endpoint

The primary efficacy endpoint will be the proportion of subjects with DAS28-ESR < 3.2 at Week 12.

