20.3.2 Secondary Efficacy Endpoints

- Proportion of subjects who maintained DAS28-ESR < 3.2 from Week 12 through Week 24.
- Time to disease activity flare from Week 12 through Week 24.
- Proportion of subjects with CDAI \leq 10 at Week 12.
- Proportion of subjects who meet criteria for ACR20 at Week 12.

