20.6 Interim Analysis

The study results from Part 1 will be summarized when all subjects complete the Part 1 of the study. No other interim analyses are planned for this study.

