20.7 Statistical Power and Sample Size Considerations

It is expected that 360 subjects will be screened and a total of 232 subjects will be enrolled in this study. It is estimated that 55% of subjects will either drop out before Week 12 or will not achieve LDA by Week 12. The remaining 45% of subjects will have achieved LDA after 12 weeks of treatment with Acthar and will be randomized into 2 treatment groups in Part 2 of the study. Based on results from previous studies ([Pincus, 2011](#)) and ([Ruperto et al, 2008](#)), it is estimated that 80% of the Acthar group and 50% of the placebo group will maintain LDA after the 12 additional weeks of treatment. Assuming that 52 subjects per group (104 subjects total) will complete Part 2, and based on the use of a 2-sided, 2-sample comparison of proportions at the $\alpha = 0.05$ level of significance, there will be 90% of power to detect a difference in the 2 treatment groups.

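### Should study success rest on the uncontrolled Week 12 response rate when the 232 subjects are sized on the randomised Part 2 comparison?

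*Combined protocol and SAP*

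**What the plan says.** The primary endpoint (section 20.3.1) is "the proportion of subjects with DAS28-ESR < 3.2 at Week 12". It is measured in a period without a control group. Section 11.1 states: "During the first part of the study (Part 1-Open Label Period) all enrolled subjects will be treated with Acthar". The synopsis attaches the success rule to this rate: "The study will be deemed successful if the lower bound of the 95% confidence interval is $\geq 10" percent. It sets no condition on Part 2.

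The sample size in section 20.7 starts elsewhere. It expects 232 enrolled and says: "The remaining 45% of subjects will have achieved LDA after 12 weeks of treatment with Acthar and will be randomized". It then assumes that 80% on Acthar and 50% on placebo maintain LDA, with 52 per group, and concludes that "there will be 90% of power to detect a difference in the 2 treatment groups". That comparison serves a secondary endpoint (section 20.3.2): "Proportion of subjects who maintained DAS28-ESR < 3.2 from Week 12 through Week 24". The synopsis tests it with a two-sided Pearson chi-square at 0.05.

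Two further provisions bear on the point. On timing, section 20.6 says: "The study results from Part 1 will be summarized when all subjects complete the Part 1 of the study". On entry, section 12.1 requires: "Subjects must have persistently active RA defined as a DAS28-ESR > 3.2 despite treatment".

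**The concern.** The one controlled comparison, and the one that fixes the sample size, has no role in the decision about success. That decision rests on a single-arm rate and a bar that the planned response rate clears about three times over. A study with an unremarkable or null Part 2 would still be called successful. Because Part 1 is summarised once all subjects have finished it, that label could be available before the last randomised subjects reach Week 24.

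Entry and response also share the cut-off of 3.2, with no minimum fall required. Some counted responders might therefore reflect fluctuation of the score or the expectations that go with open-label treatment. At stake is whether a reader would take the word successful as evidence that Acthar beats placebo, which the rule does not test.

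**Working it through.** **1. The plan's own figure.** Inputs from section 20.7: 80% v 50%, two-sided alpha 0.05, 90% power, 45% reaching LDA. With pooled variance under the null and mean rate 0.65:

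n per group = [1.96 × √(2 × 0.65 × 0.35) + 1.2816 × √(0.8 × 0.2 + 0.5 × 0.5)]² / 0.30² = 51.01, rounded up to 52.

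Power at 52 per group is 90.6% by this formula and 91.0% by exact enumeration of the Pearson test. Enrolment: 104 / 0.45 = 231.1, hence 232. All stated figures reproduce.

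**2. The count that meets the 10% bar**, with all 232 in the mITT population. The available text names no interval method.

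| Interval | Lower bound at 33/232 | Lower bound at 34/232 | Responders needed |
|---|---|---|---|
| Wilson | 10.31% | 10.68% | 33 (14.2%) |
| Clopper-Pearson | 9.998% | 10.37% | 34 (14.7%) |
| Wald | 9.73% | 10.10% | 34 (14.7%) |

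The expected count is 0.45 × 232 = 104.4, so the choice of interval matters only if the result falls at exactly 33.

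**3. Operating characteristics of the rule.** With X ~ Binomial(232, p):

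| True rate p | P(X ≥ 33) | P(X ≥ 34) |
|---|---|---|
| 10% | 2.5% | 1.6% |
| 15% | 66% | 59% |
| 20% | 99.1% | 98.6% |
| 45% | about 100% | about 100% |

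At a true rate equal to the bar, the error rate is what a two-sided 95% interval should give on one side. The near-certain pass at 45% means that Part 1 has more subjects than its own endpoint needs. It does not mean that the rule is invalid.

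**4. What requiring both results would do.** Take X ≥ 34 and a Part 2 chi-square significant in favour of Acthar, with responders split 1:1 and all randomised subjects analysed.

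| Scenario | Part 1 rule alone | Both required |
|---|---|---|
| LDA 45%, maintained 80% v 50% | about 100% | 91% |
| LDA 30%, maintained 80% v 50% | about 100% | 77% |
| LDA 20%, maintained 80% v 50% | 98.6% | 58% |
| LDA 45%, equal maintenance (50%, 65% or 80% in both arms) | about 100% | 2.5% to 2.6% |

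The 91% allows for no loss in Part 2. The plan expects about 104 randomised and also assumes that 104 complete. If 10%, 15% or 20% drop out of each arm and count as not maintained (an assumption; the documents give no rate), the maintained proportions become 72% v 45%, 68% v 42.5% and 64% v 40%. Success on both then falls to 81%, 76% and 70%.

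**5. Whether Part 2 can stand in for the missing control.** Part 2 randomises only subjects already in LDA on Acthar. It asks whether continuing beats stopping. Equal maintenance would also arise if Acthar induced LDA and the response outlasted withdrawal. The last row of the table in step 4 is therefore not a count of false successes. It includes trials of a drug that did what the primary objective asks.

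**6. Fluctuation around 3.2.** A model with 36 combinations of assumed inputs was tried: underlying mean 3.8 to 5.0, between-subject SD 0.8 to 1.2, within-subject SD 0.4 to 0.8, and entry above 3.2 at both Screening and Baseline. With no real change, fluctuation alone reached 34/232 in 1 of the 36, and in none once 10% dropout counted as non-response. More combinations reach the bar only when an average open-label improvement is assumed: 9 with a shift of 0.3 and 23 with a shift of 0.6. The documents supply none of these inputs.

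**The case for a change.** The strongest case for a change is that the success sentence speaks of the study, not of Part 1, and so invites a comparative reading that the result cannot bear. Success needs about a third of the planned response rate. With 34 responders, Part 2 would have 17 per group and about 46% exact power for 80% v 50%, and the study would still be successful. Relabelling the outcome as a Part 1 criterion would cost only wording.

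The facts in this stand, but they do not make the plan wrong. Section 10.1 asks about 12-week efficacy by DAS28-ESR, section 10.2 places maintenance second, and the success rule follows that order. Sizing enrolment on the more demanding secondary comparison leaves both questions well powered at the planned rates. The Part 2 test is specified in advance and reported in its own right, so a null result would be visible. The timing point is partly inference: section 20.6 says that Part 1 is summarised, not that success is declared then. A new label would change no analysis, estimate or decision. The interval method and the basis for 10% may be in parts of section 20 that are not available, so neither can be called absent. The ACR20 endpoint at Week 12 already requires a real improvement, which partly meets the point about a minimum fall.

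**Conclusion.** No change to the plan follows. The observation is accurate: enrolment is driven by Part 2, success by an uncontrolled Part 1 rate, and 33 or 34 of 232 suffice against about 104 expected. It describes a choice that agrees with the stated objectives. The rule has a sound error rate against 10% (1.6% to 2.5%), and the 90% power statement is correct.

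Making Part 2 a co-primary requirement is a trade-off, not a correction. It promotes a secondary objective, answers maintenance and not induction, and lowers the chance of success from about 100% to 91% at the planned rates, or to between 70% and 81% under the assumed Part 2 dropout. Relabelling the outcome, or tabulating responders by size of fall, would aid reading but alter no conclusion. Whoever reports the trial should in any case present the Part 1 result as non-comparative, because the design admits nothing else.

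The counts assume that all 232 are in the mITT population; a smaller population lowers them slightly (30 or 31 of 209, if 10% were lost).

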22 SUBJECT DISCONTINUATION OR WITHDRAWAL

22.1 Subject Withdrawal

Subjects who discontinue, or are withdrawn from the study for any reason, will be required to enter the follow-up period and have the Early Termination and Follow-up safety assessments (see [Section 14.5](#) and [Section 14.6](#)) to assess their continued well-being.

The reason for discontinuation will be recorded. A subject may be discontinued from the study for the following medical or administrative reasons:

Withdrawal by Subject

Subjects will be free to discontinue from the study at any time. Subjects who have received at least 1 dose of study drug but do not complete the study will not be replaced.

Adverse Event

If a dosed subject suffers an AE that, in the judgment of the investigator, sponsor or MM, presents an unacceptable consequence or risk to the subject, the subject will be discontinued from further participation in the study. In addition, adverse events outlined in [Section 15.3.1](#) will require subject withdrawal.

Death

In the event that a subject dies during the study, death will be the reason for discontinuation.

Lost to Follow-up

Every effort should be used to maintain contact with subjects during their participation in the study. A subject may be considered lost to follow-up if there is no response to 3 attempts to reach the subject by telephone and no response to a certified letter sent to the last known address of the subject. Efforts to contact the subject should be noted in source documentation.

Met Withdrawal Criteria

If a subject develops a condition that meets any of the exclusion criteria ([Section 12.2](#)) or fails to meet an inclusion criteria ([Section 12.1](#)) during the study that is not considered to be an AE or is noncompliant (eg, has a positive pregnancy or drug screening test), the subject will be discontinued from further participation in the study. Discontinuation is also mandated for safety and/or tolerability issues as outlined in [Section 15.3.1](#).

Worsening of Disease Activity

Subjects will be withdrawn if they have a flare/worsening of disease activity defined as:

- **Weeks 0 to 11:** DAS28-ESR ≥ 3.2 and increase of > 0.6 from the Week 0 assessment sustained over 2 consecutive study visits; **or** DAS28-ESR ≥ 3.2 and increased of > 1 from the Week 0 assessment at a single visit.

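### Is the trial at fault because Part 1 can succeed with about 34 responders of 232 while the powered Part 2 comparison needs 104?

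*Combined protocol and SAP*

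**What the plan says.** The primary endpoint (section 20.3.1) is the proportion with DAS28-ESR below 3.2 at Week 12 of open-label treatment. On its analysis the synopsis says "The lower bound of the 95% confidence interval will be used to evaluate the response rate", and then "The study will be deemed successful if the lower bound of the 95% confidence interval is" 10% or more. Section 11.1 gives the purpose of Part 1 as "to assess the proportion of subjects who achieve LDA".

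Only subjects with LDA at Week 12 are randomized, 1:1, to Acthar or placebo for 12 more weeks (section 11.1). Maintaining LDA is a secondary objective (section 10.2) and a secondary endpoint (section 20.3.2).

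Section 20.7 bases the sample size on Part 2. It takes 55% as lost or not in LDA by Week 12, and continues: "The remaining 45% of subjects will have achieved LDA after 12 weeks of treatment with Acthar". It assumes that 80% on Acthar and 50% on placebo maintain LDA. It then states 90% power, at a two-sided 0.05 level, with this condition: "Assuming that 52 subjects per group (104 subjects total) will complete Part 2".

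On numbers, section 11.1 says "Approximately 232 subjects will be enrolled". Section 20.6 plans a summary of Part 1 and adds "No other interim analyses are planned for this study". Section 22.1, under withdrawal by the subject, says "Subjects who have received at least 1 dose of study drug but do not complete the study will not be replaced".

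**The concern.** The two parts draw on the same 232 subjects but make very different demands of them. Part 1 needs about 34 responders. Part 2 needs 104, and its size is simply 232 times the LDA rate. Any rate between about 15% and 45% would count as a successful study while the only placebo-controlled comparison fell below its stated power.

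The 45% also looks exposed. The two studies cited in section 20.7 are attached to the 80% and 50%, and no source is shown for 45%. The only LDA rate for Acthar in the documents is half of 10 newly diagnosed subjects, measured by CDAI (section 9.1). No visible rule extends enrolment if responders are fewer than expected. If so, a non-significant maintenance result could reflect too few randomized subjects rather than the absence of an effect.

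**Working it through.** **Inputs.** From section 20.7: 232 enrolled, 45% in LDA at Week 12, 80% v 50% maintaining LDA, 52 per group, two-sided alpha 0.05, 90% power. From the synopsis: Pearson chi-square test, and a 10% bar for the lower 95% limit. From section 11.1: 1:1 allocation. LDA rates other than 45% are assumptions; the documents give none.

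**1. The plan's own figure.** 232 x 0.45 = 104.4, so 104 randomized and 52 per group. With the pooled rate (0.80 + 0.50)/2 = 0.65, the usual formula is

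power = Phi{ [0.30 - 1.96 x sqrt(2 x 0.65 x 0.35 / n)] / sqrt[(0.80 x 0.20 + 0.50 x 0.50) / n] }.

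At n = 52: [0.30 - 1.96 x 0.09354] / 0.08880 = 1.314, and Phi(1.314) = 90.6%. Exact enumeration of the uncorrected chi-square test gives 91.0%. The stated 90% reproduces.

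**2. The Part 1 cut-off.** The smallest count of 232 whose lower 95% limit reaches 10% is 34 by Clopper-Pearson (34 gives 10.37%, 33 gives 9.998%) and by Wald, and 33 by Wilson. 34/232 = 14.7%.

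**3. Both parts at other LDA rates, 232 enrolled.** The number randomized is 232 x rate. Formula power uses half that number per group. The last power column is exact chi-square power averaged over the binomial number of responders.

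| True LDA rate | Expected randomized | Part 1 passes (34 or more) | Part 2 power, formula | Part 2 power, exact, averaged |
|---|---|---|---|---|
| 45% | 104.4 | >99.9% | 90.7% | 90.8% |
| 40% | 92.8 | >99.9% | 87.0% | 87% |
| 35% | 81.2 | >99.9% | 82.1% | 83% |
| 30% | 69.6 | >99.9% | 75.8% | 76% |
| 25% | 58.0 | >99.9% | 67.7% | 69% |
| 20% | 46.4 | 98.55% | 57.6% | 59% |

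At a true 45%, chance alone gives fewer than 104 randomized 45% of the time, but most such shortfalls are small. Average power is still 90.8%, so this is no weakness in the 90%.

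**4. How firm is the doubt about 45%?** Five of 10 has an exact 95% interval of 18.7% to 81.3%. It cannot support 45%, but its centre lies above 45%, and it gives no ground for expecting 20-30%.

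**5. What a rule to enrol until 104 are randomized would buy.** Take a minimum of 232 and a cap of 350. By simulation:

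| True LDA rate | Mean enrolled | Part 2 power |
|---|---|---|
| 45% | 238 | 92% |
| 40% | 261 | 91% |
| 35% | 297 | 91% |
| 30% | 337 | 90% |
| 25% | 350 | 85% |
| 20% | 350 | 77% |

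These figures ignore the 12-week wait before response is known. Assume even accrual over about 47 months (4.5 years, or 54 months, from section 11.3, less about 7 months for the 32 weeks of participation in section 11.2). Then 12 weeks, about 2.8 months, holds 232 x 2.8/47, or about 14 subjects still in Part 1. With that lag, mean enrolment rises to about 247 at 45% and 274 at 40%.

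To reach 104 randomized at 30%, 25% or 20% takes 104/0.30 = 347, 104/0.25 = 416 or 104/0.20 = 520 subjects.

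**The case for a change.** The strongest case for acting is that Part 2 is the trial's only randomized, placebo-controlled evidence and the sole visible basis for enrolling 232. The responder count comes from open-label data before randomization, so it can be watched without touching any Part 2 outcome, and IXRS already calculates DAS28-ESR (section 15.1). If 45% is right, an extension rule costs little. The 104 are also described as subjects who complete Part 2, yet they equal everyone expected to be randomized, so nothing is allowed for loss. If 10% were lost and excluded (an assumption), 46.8 per group would remain and power would be about 87%.

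Much of this stands as description. The 90% is conditional on 45% LDA and on essentially no Part 2 loss, and the two parts do have unequal thresholds. It does not amount to a defect:

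- A success rule tied to the primary endpoint follows from the order of objectives in sections 10.1 and 10.2. The plan nowhere claims that passing Part 1 secures Part 2.
- Any design that randomizes only responders has a Part 2 size that depends on the response rate.
- The figure of 232 is given as approximate or expected (sections 11.1, 11.4 and 20.7), not as a ceiling, and section 24 allows amendments. The non-replacement sentence concerns withdrawals, not a low response rate.
- Extension puts more subjects on open-label treatment and makes the primary denominator depend on response, all for a secondary endpoint. As framed it also counts randomized rather than completing subjects.
- Sections 20.1, 20.4 and 20.5 appear in the contents list but not in the public text, and section 20.3.7 shows only two sentences. The confidence-interval method and the origin of the 10% bar cannot be called missing from the plan.

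**Conclusion.** No change is needed. The 90% power is right for 52 per group, 80% v 50% and a two-sided 0.05 level, and 232 x 0.45 gives the 104 it uses. The gap between 34 and 104 responders reflects a primary and a secondary aim of different kinds, not a contradiction.

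The exposure is real but conditional. Part 2 power would be about 87% at 40% LDA, 83% at 35%, 76% at 30%, 69% at 25% and 59% at 20%. These figures assume 232 enrolled, the plan's 80% v 50%, and no Part 2 loss. The lower rates are hypothetical; the documents point to none of them. Protecting Part 2 against them would take up to 118 more subjects with a cap of 350 and would still leave 85% power at 25% and 77% at 20%. Declining that price for a secondary endpoint is a fair trade-off.

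A table of power by LDA rate in section 20.7 would put the dependence on record but would alter no analysis or result. If responders prove few, a reader can see the number randomized and the width of the Part 2 interval, and can judge a non-significant comparison accordingly.
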